## 6.6. Exploratory analysis

## Assessing the hypothesised mechanisms of change and influence of school context

In keeping with the study's logic model and hypothesised mechanisms of change, logistic regression models will be used to compare binary measures of stress and satisfaction at work, support given / received at school, school's perceived attitude to staff and student wellbeing and perceived quality of relationships in school between arms at follow up, adjusted for baseline scores, school-level FSM and geographical area. We will also examine whether baseline measures of these variables – which provide indicators of school psychosocial context - moderate the effect of the intervention by including interaction terms between these baseline variables and intervention arm in the analysis model.

Appropriate mixed models will be applied as for the primary analysis (see section 6.2, paragraph 1), but additionally including measures of these mechanisms as covariates. We will assess the degree to which the estimated treatment effect attenuates compared with our chief analysis model – substantial attenuation would indicate the proposed mechanisms of change are indeed acting as such. However, this is subject to accurate measurement of the proposed mechanism of change and the lack of confounding variables influencing the relationship between mechanism and outcome [12].

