## 2.1.2. Secondary objectives

 Does the WISE intervention lead to lower levels of teacher depression, absence and presenteeism, improved student wellbeing, attendance and attainment, and reduced student mental health difficulties compared to usual practice?

- Do any effects of the intervention differ according to the proportion of children receiving free school meals (FSM – an indicator of the socioeconomic catchment area) and geographical area, or individual level baseline mental health, gender, ethnicity and FSM?
- 3. What is the cost of the WISE intervention, and is it justified by improvements to staff and student wellbeing and reductions to staff depression and student difficulties?
- 4. Does the WISE intervention work according to the mechanisms of change hypothesised in the logic model?
- 5. Is the WISE intervention sustainable?

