## 6.3. Secondary analyses

The primary analysis (i.e. mixed effects repeated measures model including every teacher who has at least one measure of the outcome i.e. at baseline, one or two year follow up) will be repeated with a treatment by time interaction term added to the model. This will allow estimation of treatment effect at 12 and 24 month follow ups separately. Analysis of secondary outcomes will include linear, ordinal and logistic regression models dependent on the nature of the outcome variable being analysed (continuous, ordinal or binary respectively).

For secondary individual level outcomes that are measured at baseline, 12 and 24 months (e.g. PHQ-8), repeated measures models will be used, these models will include random effects for clustering by individual (due to repeated measure) and by school. All individuals with at least one observation of the outcome measure will be included in the model for that outcome measure using maximum likelihood under a Missing at Random (MAR) assumption. For each secondary individual level outcome that are measured at baseline, 12 and 24 months, 3 models will be presented:

- Model 1: Unadjusted model Repeated measures of the outcome regressed on treatment arm accounting for clustering due to repeated measures and by school (using random effects).
- Model 2: Partially adjusted model Model 1 plus adjustment for stratification variables.
- Model 3: Fully adjusted model Model 2 plus additional adjustment for covariates. For teacher based outcomes the covariates adjusted for will be sex and years of experience, for student based outcomes sex and ethnicity will be included as covariates.

For each secondary individual level outcome measured only at baseline and 24 months, 3 models will be presented:

- Model 1: Unadjusted model Outcome at 24 months regressed on treatment arm and baseline value of the outcome, accounting for clustering by school (using a random effect).
- Model 2: Partially adjusted model Model 1 plus adjustment for stratification variables.
- Model 3: Fully adjusted model Model 2 plus additional adjustment for covariates. For teacher based outcomes the covariates adjusted for will be sex and years of experience, for student based outcomes sex and ethnicity will be included as covariates.

For each secondary school level outcome measured only at baseline and 24 months, 2 models will be presented:

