## 8. FINAL REPORT TABLES AND FIGURES

## 8.1. Subject characteristics and background summaries

Table 1. Baseline Characteristics for Teachers

	Con	trol		Intervention		
Variables (Teacher)	Ν	Mean/%	SD	Ν	Mean/%	SD
Male (%)						
WEMWBS						
PHQ-8 score						
Presenteeism Score						
Average days Absent past 4 weeks						
Absence (ever/never)						
Previous mental health problem						
Previous MH training						
• Yes						
• No						
Can't remember						
Job satisfaction (%)						
Very satisfied						
Satisfied						
A little dissatisfied						
Dissatisfied						
Highly dissatisfied						
Job stressfulness (%)						
Not at all stressful						
Mildly stressful						
Moderately stressful						
Very stressful						
Extremely stressful						
Experience with school environment						
• < 1 year						
• 1-2 years						
• 3-5 years						
• 6-10 years						

 
> 10 years
 
						
Ethnicity (%):						
White						
Mixed						
Asian or Asian British						
Black or black British						
Chinese						
Wanted to seek help from colleague due to						
stress (%)						
Never						
Once or twice						
Once a term						
Once or twice a month						
Once or twice a week						
Every day						
Haven't felt stressed or down						
Good relationship between students and						
teachers (%)						
Strongly agree						

 
Agr
 
	ree			
• Un:	isure			
• Dis	sagree			
• Str	ongly disagree			
Good relation	onship between staff (%)			
• Str	ongly agree			

 
Agr
 
	ree			
• Un	isure			
• Dis	sagree			
• Str	ongly disagree			

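### Section 6.6 compares the mechanism-of-change items between arms only as binary variables with no stated cut, although Table 1 shows several of them on five ordered levels: an avoidable loss of precision in an exploratory analysis

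*SAP*

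**What the plan says.** Secondary objective 4 (SAP 2.1.2) asks: "Does the WISE intervention work according to the mechanisms of change hypothesised in the logic model". The analysis that answers it is under "6.6. Exploratory analysis". Its first paragraph states that "logistic regression models will be used to compare binary measures of stress and satisfaction at work", and adds support given or received, the school's perceived attitude to wellbeing, and the perceived quality of relationships. The arms are compared at follow-up with adjustment for baseline scores, school-level FSM and geographical area. No cut-point is given for any item.

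Table 1 (SAP 8.1) lists the teacher response options. "Job satisfaction" and "Job stressfulness" have five ordered levels each. So do the two relationship items, one between staff and one between students and teachers. The student relationship item in Table 2 has four levels.

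Ordinal models are already in use elsewhere in the SAP. Section 6.3 states: "Analysis of secondary outcomes will include linear, ordinal and logistic regression models dependent on the nature of the outcome variable being analysed". Section 2.10.2 gives PHQ-8, absence and presenteeism both ordinal and binary versions, with the cuts written down.

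**The concern.** Cutting a five-level item in two treats every move on one side of the cut as no change. If job stress is split between its third and fourth levels, a teacher who goes from extremely to very stressful counts as unchanged.

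This is the plan's direct between-arm test of whether the intervention moved the mechanisms. If precision is thrown away here, a real shift is more easily reported as a mechanism that did not change, and that reading then colours the explanation of the primary result.

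The missing cut adds to the problem. A five-level item can be split in four ways, and both the result and the precision depend on which is used. A full-scale analysis removes that choice along with the loss.

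**Working it through.** **1. The plan's own power figures, for reference.** These concern teacher WEMWBS only (SAP 2.7): difference 3, SD 8.4, 12 schools per arm, mean 50 teachers, coefficient of variation 0.5. A two-sided 5% level is assumed from the 95% interval in section 6.2.

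- Design effect = 1 + ((1 + 0.5²) × 50 − 1) × ICC = 1 + 61.5 × ICC. At ICC 0.05 this is 4.075.
- Effective number per arm = 600 / 4.075 = 147.2.
- Standard error = 8.4 × √(2/147.2) = 0.979, so 3 / 0.979 = 3.06.
- Noncentral t power on 22 df is 83.4%. The same steps give 97.7% at ICC 0.02 and 68.1% at ICC 0.08.

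The SAP states over 80%, 98% and 68%, so its figures reproduce. It states no power for any mechanism item.

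**2. Efficiency of a binary split against the full scale (small effects, no clustering).** With category shares p and a cut that puts share q on one side, relative efficiency = 3q(1 − q) / (1 − Σp³). Two assumed distributions:

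- Five equal shares of 20%: 1 − Σp³ = 0.96. Cut at 40%: 3 × 0.4 × 0.6 / 0.96 = 0.75. Cut at 20%: 3 × 0.2 × 0.8 / 0.96 = 0.50.
- Shares 7/13/25/40/15%: 1 − Σp³ = 0.914. Cut at 45%: 3 × 0.45 × 0.55 / 0.914 = 0.81. Cut at 7%: 3 × 0.07 × 0.93 / 0.914 = 0.21.

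**3. From efficiency to power.** Power of the binary analysis = Φ((1.96 + z) × √RE − 1.96), where z = 0.842 for a full-scale power of 80% and 1.282 for 90%.

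- RE 0.70: 80% falls to 65%, 90% to 77%.
- RE 0.75: 80% falls to 68%, 90% to 80%.
- RE 0.81: 80% falls to 71%, 90% to 83%.

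**4. The same comparison at the trial's effective size.** Whitehead's proportional-odds information was computed at the effective number per arm. The odds ratio was set so that the five-level analysis has 80% power, and every cut was then tried. Results at ICC 0.05, with assumed distributions:

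| Assumed shares (%) | RE, best cut | Loss, best cut (points) | Loss, second-best cut | Loss, worst cut |
|---|---|---|---|---|
| 20/20/20/20/20 | 0.78 | 10 | 15 | 35 |
| 10/20/40/20/10 | 0.76 | 12 | 21 | 52 |
| 15/45/25/10/5 | 0.76 | 12 | 26 | 63 |
| 3/20/42/27/8 | 0.69 | 16 | 16 | 63 |
| 25/50/15/8/2 | 0.76 | 12 | 24 | 71 |

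Over ICC 0.01 and 0.05 and reference powers of 80% and 90%, the best cut loses 8 to 16 points, the second-best 12 to 29, and the worst 32 to 79.

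**5. A rough cross-check.** A simulation of 24 schools (mean 50, CV 0.5, assumed baseline to follow-up correlation 0.5) compared a 0-4 score with its binary version by school-level t-tests. With a cut near the middle, power fell from about 79% to 69-70% at ICC 0.05, from 81% to 67% at ICC 0.02, and from 79% to 61-63% at ICC 0.01. The order of size agrees, but neither the logistic nor the proportional-odds mixed model was fitted.

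**The case against.** The strongest reply is that the section is labelled exploratory and promises no power, that percentages are easy to read, and that proportional odds brings an assumption of its own. A smaller repair would be to state the cut-points in advance. The label and the absence of a power claim limit how serious the point is. They do not give a reason to discard collected data on a listed objective. Stating the cuts would remove the free choice, but even the best cut lost about 8 points in the scenarios tried.

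Four stronger readings are tempting and are not supported:

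- **That the plan contradicts itself.** A reader might infer this from section 6.3. Its rule covers secondary outcomes, and the mechanism items are not among those listed in 2.10.2. Once an item is defined as binary, logistic regression fits the rule. Section 6.3 shows only that ordinal models are within the plan's repertoire.
- **That information is lost in the baseline covariate too.** Section 6.6 speaks of baseline scores and does not say that they are dichotomised. In a simulation of the kind above, using the full five-level baseline with a binary outcome recovered only about 1 to 2 points.
- **That every mechanism measure is a collapsed five-level scale.** No scale is shown for support given or received, or for school attitude. The Table 1 item beginning "Wanted to seek help from colleague due to" is not named in section 6.6, and wanting help is not the same as giving or receiving support.
- **That the loss is a known number.** All power figures for these items depend on assumed distributions, cuts and effect sizes. Step 4 also applies one effective size to both analyses, which is a simplification.

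Objective 4 also does not rest on this comparison alone. The second paragraph of section 6.6 adds the mechanism measures to the primary model and looks for attenuation of the treatment effect, without saying whether those measures are binary.

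**Conclusion.** The point holds as an avoidable loss of efficiency, together with an unstated cut. Four teacher items that Table 1 shows on five ordered levels fall within measures that section 6.6 compares only in binary form. With a central cut, the binary analysis is about 0.70 to 0.81 as efficient as a proportional-odds analysis, or roughly 8 to 16 points of power from a reference of 80 to 90%. An off-centre cut costs considerably more. These sizes assume the category shares shown above, a common odds ratio across levels, and the cluster sizes and ICCs that the SAP gives for WEMWBS. No figure stated in the SAP is wrong. Because the analysis is exploratory, what is at risk is the reading of the mechanisms; the primary conclusion is unaffected.

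**What to change.** In section 6.6, for each mechanism item recorded in ordered categories, make the between-arm comparison a proportional-odds mixed model with a random effect for school. Adjust for the item's full-scale baseline value, school-level FSM and geographical area. Keep logistic regression for items that are truly yes/no, and show binary percentages as description only.

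The cost is revised wording and a change of model command, with no new data. The proportional-odds assumption has to be checked for each item, and a common odds ratio is slightly harder to explain than a difference in percentages.

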#### 2.7. Sample size and justification

The primary outcome measure will be the WEMWBS scale. A change of 3 points on this scale is close to the difference in mean scores between the highest and lowest ranked schools in the pilot study. The sample size takes account of clustering; in the pilot data from 6 schools, the WEMWBS ICC (calculated using the loneway command in Stata) for teachers was 0.01 (95%Cl 0.00, 0.05) [1]. We assume a mean of 50 teachers followed up per school after allowance for 20% dropout (with a coefficient of variation of sample size of 0.5), and an SD for WEMWBS of 8.4 (based on the pilot data). Given that estimates based on pilot data can be unreliable [2], assuming an ICC of 0.05, which is greater than that seen in the pilot, -a sample size of 24 schools (12 intervention and 12 control) would achieve over 80% power. This would rise to 98% if the ICC is 0.02, and fall to 68% for an ICC of 0.08. These estimates of power are likely to be conservative given that the sample size calculation does not account for the baseline assessment of the outcome.

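### SAP 6.6 tests school psychosocial context as an effect modifier without defining a school-level measure; on the natural reading the term mostly captures differences in perception between colleagues

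*SAP*

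**What the plan says.** The relevant part of SAP section 6.6 is headed "Assessing the hypothesised mechanisms of change and influence of school context". It first compares the arms at follow-up, by logistic regression, on "binary measures of stress and satisfaction at work, support given / received at school", together with perceived school attitude and perceived relationships. These models are "adjusted for baseline scores, school-level FSM and geographical area".

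It then turns to moderation. It will examine whether baseline versions of the same items, "which provide indicators of school psychosocial context - moderate the effect of the intervention by including interaction terms between these baseline variables" and trial arm. The text specifies no school mean, school percentage or split into between-school and within-school parts. It does not name the outcome whose treatment effect is being moderated.

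**The concern.** Context is a property of the school: colleagues share it. A single teacher's answer mixes that shared part with the teacher's own view. If the answer itself is the moderator, a model with one interaction term is driven mainly by contrasts between colleagues, who by definition have the same context.

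Two misreadings could follow. A real dependence of the effect on school context could look like no moderation. A real dependence on individual perception could be reported as an effect of school context. Nor would a wide confidence interval warn the reader, because the individual-level term can look precise while answering a different question.

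There is also a reproducibility issue. Section 1 intends the plan to let someone else carry out the analysis. Here two analysts could follow the text and test different constructs.

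**Working it through.** **Which level does the text imply?**
- The items are first modelled as individual binary outcomes with baseline adjustment, and the moderators are the baseline versions of those items.
- In that sentence only free school meals (FSM) is marked as school-level. Section 6.5 likewise separates school FSM from individual FSM.
- Job satisfaction, job stressfulness and relationship items appear in "Table 1. Baseline Characteristics for Teachers". None appear in the school table (Table 3).
- Elsewhere in 6.6, one of the Reach factors classifies schools by their teachers' questionnaire answers relative to the study mean. No such step is given for the context items.

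Individual entry is therefore the natural reading, but it is an inference.

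**The plan's own figure.** Section 2.7 states that a "sample size of 24 schools (12 intervention and 12 control) would achieve over 80% power" at ICC 0.05, with 98% at 0.02 and 68% at 0.08. Inputs from 2.7: m = 50 teachers per school, CV of cluster size 0.5, SD 8.4, difference 3 points. A two-sided 5% test is assumed.
- Design effect = 1 + [(1 + CV²)m − 1] × ICC = 1 + 61.5 × 0.05 = 4.075.
- Effective n per arm = 600/4.075 = 147.2; SE = 8.4 × √(2/147.2) = 0.979.
- Power by noncentral t on 22 df = 83.4%. The same steps give 97.7% at ICC 0.02 and 68.1% at 0.08.

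The stated power reproduces. The SAP gives no figure for the moderation test.

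**How much school-level moderation would an individual rating recover?** Write the rating as a school part plus a teacher part, with a share ρx of its variance between schools (the rating ICC). Let the treatment effect depend on the school part only. Then the within-school interaction slope is 0, and the between-school slope is reduced by the reliability of the school mean, λ = mρx/[1 + (m−1)ρx]. With outcome ICC ρy, a random-intercept model weights the two slopes by
- between: W_B = [1 + (m−1)ρx]/[1 + (m−1)ρy]
- within: W_W = (m−1)(1−ρx)/(1−ρy)

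and the share recovered is λ·W_B/(W_B + W_W).

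Example with ρx = ρy = 0.05:
- W_B = 3.45/3.45 = 1
- W_W = 46.55/0.95 = 49
- between-school weight = 1/50 = 0.02
- λ = 2.5/3.45 = 0.725
- share = 0.02 × 0.725 = 1.45%

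| Rating ICC (assumed) | Individual rating, outcome ICC 0.05 | Individual rating, outcome ICC 0.01 | School mean (λ) |
|---|---|---|---|
| 0.05 | 1.5% | 3.4% | 72% |
| 0.10 | 3.0% | 6.9% | 85% |
| 0.20 | 6.5% | 14.3% | 93% |

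Outcome ICC 0.05 is the planning value and 0.01 the pilot estimate, both from 2.7. All slopes are per unit of the rating. Dividing a slope per individual-rating SD by one per school-level SD would mix scales.

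**Simulation with binary items.** Settings: 24 schools, mean size 50, CV 0.5, one follow-up score per teacher, variance components treated as known, about 1,000 runs per scenario. The true treatment effect differed by 4 points between schools above and below the median of true context. The rating ICC, on the latent scale, ran from 0.02 to 0.20.

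| Outcome ICC | Individual rating: mean coefficient; rejection | Split on school mean: mean coefficient; rejection |
|---|---|---|
| 0.05 | 0.09-0.32; 5-7% | 1.75-2.89; 16-29% |
| 0.01 | 0.24-0.76; 6-14% | 1.67-3.06; 31-62% |

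The individual coefficient contrasts teachers by their own answer, so it is not on the same contrast as the 4 points. The rejection rates are the fairer comparison. At the planning ICC the individual term rejects at close to its nominal 5%.

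**The case against.** **The SAP does not say that each teacher's own rating is entered.** A reader might infer that it does. The text leaves the level open, so the exact fault is that the level is unspecified and that the text as written leads to individual entry.

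**The loss is conditional.** A reader might infer that the plan would erase nearly all true moderation. That needs moderation to act only through shared context, and a rating ICC that the SAP does not give. At rating ICC 0.30 and outcome ICC 0.01 about 22% survives. Moderation by a teacher's own experience of the school is a sensible question, since the same items are hypothesised mechanisms, and individual entry would estimate it properly. What stands against the plan then is the label.

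**The term need not be a proxy for mood.** A reader might suppose that it repeats the baseline WEMWBS and PHQ-8 interactions in 6.5. Nothing in the SAP shows that perceived attitude, support or relationships duplicate those scores.

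**Some school-level moderation is already planned.** Section 6.5 tests school FSM and geographical area. That is true, but neither is psychosocial context.

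**Aggregation does not rescue power.** This stands. At outcome ICC 0.05, a 4-point moderation, larger than the whole 3-point planning difference, is detected in only 16-29% of simulated trials. The school mean corrects what is being estimated, not how precisely.

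**Conclusion.** The point holds in a limited form. Section 6.6 names a school-level construct and defines no school-level measure for it. On the natural reading, the interaction mostly reflects differences in perception between colleagues and should not be reported as an effect of school context.

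The recovery figures (about 1.5-6.5% at outcome ICC 0.05 and 3-14% at 0.01, against 72-93% for the school mean) rest on four assumptions: purely contextual moderation, 50 teachers per school, a random-intercept model with a single interaction term, and a rating ICC between 0.05 and 0.20. The direction does not depend on the exact ICC within that range; the size does.

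Severity is minor. One exploratory analysis is affected. The primary model, the secondary models and the subgroup tests in 6.5 are not.

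**What to change.** In section 6.6:
- Derive, for each baseline item, the school mean (for a binary item, the school percentage) and enter arm by school mean as the context moderator. Assign it to every teacher in the school, including those without a baseline form. The primary model in 6.2 admits such teachers, and the imputation in 3.2 does not cover these items.
- Enter arm by (teacher's rating minus school mean) as a separate term, reported as individual perception. It can be estimated only for teachers with a baseline form, so also fit the context term on all teachers.
- Name the outcome whose treatment effect is being moderated.
- State that, with 24 schools, the context interaction is imprecise and a null result is not evidence that context does not matter.

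The cost is a few sentences and one derived school-level variable per item (plus the teacher's deviation from it), from data already collected. The downside is a wide confidence interval for the context term, which is the precision that 24 schools can offer on this question.

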## 2.10. Outcome measures

## 2.10.1. Primary outcome

The primary outcome is the average effect of the intervention on mental wellbeing of teachers over the duration of follow up, measured using the self-completed WEMWBS questionnaire [4] collected at baseline, one and two year follow ups. The WEMWBS scales from 14-70 and will be analysed as a continuous variable.

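### The exploratory mechanism analysis (SAP 6.6) reads attenuation as a sign that the mechanisms act, without fixing when they are measured or allowing that wellbeing may change them

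*SAP*

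**What the plan says.** Secondary objective 4 (SAP 2.1.2) asks: "Does the WISE intervention work according to the mechanisms of change hypothesised in the logic model". Section 6.6 plans three things on mechanisms:

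- Logistic models compare the mechanisms between arms at follow-up, allowing for their baseline values. They are "binary measures of stress and satisfaction at work, support given / received at school, school's perceived attitude to staff and student wellbeing", plus how teachers rate relationships at the school.
- Baseline values of the same variables are tested as moderators.
- A mediation-type step follows: "Appropriate mixed models will be applied as for the primary analysis (see section 6.2, paragraph 1), but additionally including measures of these mechanisms as covariates". The treatment effect from this model is compared with that from the main model, and "substantial attenuation would indicate the proposed mechanisms of change are indeed acting as such".

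The next sentence limits the rule: it is "subject to accurate measurement of the proposed mechanism of change and the lack of confounding variables influencing the relationship between mechanism and outcome".

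The outcome is teacher wellbeing, "measured using the self-completed WEMWBS questionnaire [4] collected at baseline, one and two year follow ups". Section 6.6 does not state the wave of the mechanism covariates, a threshold for substantial attenuation, or an interval for it.

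**The concern.** Outcome and mechanism measures are both teacher reports, and the mechanisms are states and perceptions: stress, satisfaction, support, school attitude and relationships. A teacher whose wellbeing improves may become less stressed, more satisfied or better connected. The item is then a consequence of the outcome. Adjusting for a consequence of the outcome shrinks the arm coefficient even when the item plays no part in producing the effect, so attenuation alone cannot separate mediation from the reverse direction.

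The two stated conditions do not close this gap. An item can be measured without error, share no confounder with WEMWBS, and still be driven by WEMWBS.

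At stake is the answer to secondary objective 4. The trial could report support for its logic model on evidence that would look the same if the logic model were wrong.

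**Working it through.** **Timing.** The refitted model follows section 6.2, where WEMWBS at baseline, T1 and T2 are all outcomes. A baseline row has no earlier mechanism value to attach. Baseline mechanism values also precede allocation (SAP 2.8), so they cannot carry an effect of the intervention. Same-wave entry is therefore the natural reading, but the SAP does not state it.

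**Design inputs (SAP 2.7).** Difference 3, SD 8.4, ICC 0.05, mean 50 teachers per school, coefficient of variation 0.5, 12 schools per arm. The SAP gives no figure for attenuation, so I checked these inputs against its power statement.

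- Design effect = 1 + ((0.5² + 1) × 50 − 1) × 0.05 = 1 + 61.5 × 0.05 = 4.075.
- Standard error = 8.4 × √(2 × 4.075 / 600) = 0.979, and 3 / 0.979 = 3.06.
- A two-sided 5% test on 22 df (level and df assumed) gives 83.4% power, against over 80% stated.
- The same steps give 97.7% at ICC 0.02 (stated 98%) and 68.1% at ICC 0.08 (stated 68%).

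The inputs reproduce the plan's figures.

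**Assumptions not in the SAP.** The within-wave correlation ρ between wellbeing and each item is 0.3 to 0.6, on a latent scale for binary items. There are one to six items. Wellbeing alone drives the items, so true mediation is zero.

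**One wave, by formula.** For k continuous items caused only by the outcome, the share of the arm effect removed is kρ² / (1 + (k − 1)ρ²). With one item this is ρ²: 9%, 25% and 36% at ρ = 0.3, 0.5 and 0.6.

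The SAP specifies binary items. For a median split, the squared correlation of item and outcome is r² = (2/π)ρ², and the correlation between two items is φ = (2/π) arcsin(ρ²). The share is then approximately k r² / (1 + (k − 1)φ).

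- One item: 0.637 × 0.09 = 6%; 0.637 × 0.25 = 16%; 0.637 × 0.36 = 23%.
- Five items, ρ = 0.3: 5 × 0.0573 / (1 + 4 × 0.0574) = 23%.
- Five items, ρ = 0.6: 5 × 0.2292 / (1 + 4 × 0.2344) = 59%.

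**Two follow-up waves, by simulation.** 24 schools of 50, school and person random effects, within-person correlation 0.6 within school (assumed), binary items entered at the same wave, 60 replicates per setting. Attenuation is 1 minus the ratio of the mean arm coefficients with and without the items:

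| ρ | 1 item | 4 items | 6 items |
|---|---|---|---|
| 0.3 | 3% | 14% | 19% |
| 0.5 | 11% | 35% | 46% |
| 0.6 | 16% | 46% | 58% |

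In the last cell the coefficient falls from 3.03 to 1.28. The baseline wave was left out of this simulation.

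Across the two methods the range is about 3% to 23% for one binary item and about 14% to 59% for four to six. The upper end is not a ceiling: the one-wave formula with six items at ρ = 0.6 gives 6 × 0.2292 / (1 + 5 × 0.2344) = 63%.

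**A time-ordered model.** I regressed T2 WEMWBS on arm and the T1 item, adjusting for baseline WEMWBS and the baseline item. This used one continuous item, zero true mediation and within-person correlation 0.5 to 0.7. The false indirect share is about 2%, 6% and 10% at ρ = 0.3, 0.5 and 0.6, roughly a quarter of the 9%, 25% and 36% for the same item entered concurrently. The remainder arises because T1 wellbeing drives both the T1 item and T2 wellbeing. Adding T1 WEMWBS brings the coefficient of the T1 item to about zero.

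**The case against.** The strongest reply is that the plan is already cautious. The analysis is labelled exploratory, the rule is qualified in the next sentence, and there is no test or threshold that triggers a claim. A reader might infer that the SAP commits to declaring mediation; it does not. That stands. The qualification nevertheless lists two conditions and omits the one at issue.

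The accuracy condition also covers part of the problem. If ratings rise while actual support or relationships do not change, the mechanism has been measured inaccurately. What remains uncovered is real change caused by better wellbeing, such as lower stress or higher satisfaction.

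The size is uncertain too. The correlations are assumed, the whole association is taken to run in the reverse direction, and one weakly related item gives only 3% to 6%, which few would call substantial. This stands as a limit on magnitude. Section 6.6 does list several mechanisms, however, and the multi-item figures apply if they are entered together.

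A reader might also infer that the analysis is biased overall towards confirming the logic model. That is not shown: dichotomised, error-prone mediators can hide real mediation, and only one source of bias was examined. Nor is this rule the only evidence planned for objective 4, because section 6.6 also compares each mechanism between arms.

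**Conclusion.** The concern holds in a limited form. Section 6.6 attaches a conclusion to attenuation that attenuation cannot support by itself. It leaves the timing of the mechanism measures open, and its conditions omit direction of effect. With no mediation at all, the calculated false attenuation runs from about 3% (one weakly related binary item) to about 59% (several moderately related items), at assumed correlations of 0.3 to 0.6 and with the whole association reverse-caused.

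The documents do not support saying that the plan fixes same-wave entry. That is the natural reading, but the defect is that the wave is unstated. The consequence is confined to the exploratory mechanism conclusion. It is still worth correcting, because the written rule can give a wrong answer on a named objective and the correction is cheap.

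**What to change.** 1. State which wave's mechanism measures enter the model.
2. Report concurrent attenuation only as consistent with mediation, and add to the stated conditions that the outcome must not itself affect the mechanism measure.
3. If the mechanism items were collected at T1 (the SAP's schedule of measures does not list them by wave), add a model of T2 WEMWBS on arm and the T1 mechanism, adjusted for baseline WEMWBS and the baseline mechanism. Report the indirect effect with a 95% interval that respects clustering by school, for example from a school-level bootstrap.
4. Add a sensitivity analysis that also adjusts for T1 WEMWBS, since without it a false indirect share of about 2% to 10% remained in the check above.

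The wording changes cost almost nothing, and the models use data already collected. There are two downsides. The time-ordered model needs teachers with both T1 and T2 data, so precision is lower. Adjusting for T1 WEMWBS may also remove effect that truly runs through T1 wellbeing, so the two time-ordered estimates should be read together.
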